*** * * * * DO NOT SHIP ON FRIDAY! * * * * ***

Contact FALCC before preparing coolers for shipping. During times of potential severe storms which may interfere with usual Fed Ex schedules, it may be prudent to delay shipment to avoid potential loss of samples.

DO NOT LET PACKED COOLERS SIT AT AMBIENT TEMPERATURE FOR AN EXTENDED TIME PERIOD PRIOR TO FED EX PICK-UP

1. Assemble containers of food to be shipped: **FROZEN solid (at least OVERNIGHT at -20°C) prior to shipment.**
2. Ensure that each container is completely sealed.
3. Fill out a sample transfer form (#F001) for each cooler. Include all required information (see sample form included). Make a copy for your records.
4. Wrap **EACH** container of food in several layers of brown paper, newspaper, or other cushioning wrap. This is necessary in order to prevent container breakage during transit.
5. Place wrapped containers in the cooler, then pack wads of brown paper, newspaper or other cushioning material around each container.
6. Place a layer of brown paper, newspaper, or other cushioning material on top of containers, then add a minimum of 5 pounds of dry ice. **USE CAUTION WHEN HANDLING DRY ICE; WEAR APPROPRIATE PROTECTIVE APPAREL AND INSULATED GLOVES.**
7. Pack wads of newspaper or brown paper to fill out cooler and prevent movement.
8. Place completed **sample transfer form (#F001)**, Deviation from SOP (Form(s) #F002, if any), and completed TACs for each menu shipped in a sealed zip-lock bag (to protect from moisture), and place in cooler, on top.
9. Tightly seal around the seam of the cooler and lid with packing tape.
10. Fill out all information on the dry ice stickers (included in shipping kit) required for Federal Express shipping: Make sure to include your complete address and make sure that the dry ice weight agrees on all stickers for the same cooler.
11. Affix a pre-addressed pre-paid FedEx shipping label to the box, and send via Federal Express overnight delivery to FALCC:
[name], Dept. of Biochemistry, [name], Virginia Tech, Blacksburg,
VA 24061-0308
12. **Notify FALCC of shipment:** [contact] or [contact] or E-mail:
[contact]

5.8.5 Unit Food Sampling and Assay Plan

Documentation of unit food composition

Unit food composition will be documented by diet-center-feeding period. Fat blend composition will be documented by the diet-center twice during the study: once at the end of feeding period 2 and once during feeding period 3.

The FALCC will check that a sample was received from each unit food batch entered on the log sheets. Any deviations will be documented. The unit foods will be composited (FALCC SOP #5038) by diet-center-feeding period (no separation by unit food type will be made). Thus 12 unit food composites per feeding period will result (3 diets x 4 centers). The total number of constituent units and total weight of each composite will be documented.

Each unit food composite will be assayed for total fat, moisture, protein (Kjeldahl Nx6.25), and ash. Moisture will be determined by vacuum drying at 60°C (FALCC SOP #5002). Total fat, protein and ash will be assayed by the same methods used for diet composites (MOP Section 7). Mean total kcal (calculated from proximates) per unit and total fat %kcal will be available as calculated values.

Each fat blend sample will be assayed in triplicate for fatty acid composition, using the gas chromatographic method employed for assay of fatty acids in diets (FALCC SOP #5025). Each fatty acid (C12:0, C14:0, C16:0, C18:0, C18:1, C18:2, C18:3n-3, C20:5n-3, C20:6n-3) will be reported in weight percent, corresponding to the units in which fat blends were formulated.

5.8.6 Procedure for Collection and Shipping of Unit Foods

PROCEDURE FOR COLLECTION AND SHIPPING OF UNIT FOODS- DELTA Protocol 2 DIET MONITORING

Food Analysis Laboratory Control Center (FALCC) Standard Operating Procedure

SOP #1030
Revision: (New)

01-MAR-95

Dept. of Biochemistry and Anaerobic Microbiology
Virginia Tech
Blacksburg, VA 24061-0308

**PLEASE READ THIS PROCEDURE COMPLETELY, PRIOR TO
FOOD COLLECTION**

Scope

This procedure applies to collection of unit foods samples for DELTA Protocol 2 diet monitoring, as part of documentation of diet composition (DELTA Protocol 2 (1994-95)).

Purpose

To describe the procedure for collecting samples from unit food batches prepared for DELTA Protocol 2 and shipping the samples to FALCC for compositing and assay.

Overview

Each center will maintain a log of all unit food batch preparations for each feeding period. This log will include, for each batch, the date of preparation, unit food name, diet, and size of batch. Each center will randomly select one unit from every batch of unit food prepared for each of the three diets D, E, and F. Each of these units will be individually packaged in an airtight container (e.g. zip-lock bag), labelled, and frozen at -20°C. At the end of each feeding period, unit food samples will be shipped frozen, on dry ice, to the FALCC where they will be composited and assayed.

Materials

At Field Center:

- prepared unit foods
- freezer (-20°C or lower)
- heavy paper (e.g. brown paper or newspaper)
- dry ice
- DELTA Unit Food Batch Preparation Log

Food Collection and Shipping Materials (supplied by FALCC):

- zip-lock bags
- labels
- cryogenic marker
- fat-free powder-free gloves (disposable)
- Form #F001 (sample transfer), with example form filled out
- Forms #F002 (deviation from SOP)
- shipping cooler
- packing tape³
- Federal Express dry ice identification stickers
- pre-addressed Federal Express shipping labels (1 per cooler)

NOTE: Follow these procedures exactly. If any deviation occurs in preparation, packaging, ingredients, sampling, shipping, etc., fill out form #F002 and include it with the food shipment.

³NOTE: The FALCC will supply each Field Center with a reasonable amount of packing tape for shipping foods to the FALCC - please reserve the tape for this use only.

**TAKE THE SAME CARE SERVING AND PACKING FOODS FOR ASSAY AS YOU
DO FOR FOODS FOR PATIENTS.**

Receipt of Shipping Materials:

Make sure you received all items listed above. If there is a discrepancy or if you should need additional labels or supplies, immediately notify the FALCC at [name], or [contact] or E-mail: [contact].

Documentation of Unit Food Batch Preparation

The purpose of batch documentation is to facilitate ensuring that all batches prepared are sampled and included in the assay composite. The "Unit Food Batch Preparation Log" serves this purpose.

1. At the time a batch of unit food is prepared, do the following:

Record the date of preparation, batch ID number (if any), the unit food name, diet, and batch size (e.g. total number of units or total weight), and your initials.

2. Maintain the preparation log at your center, and send a copy to the FALCC with the shipment of unit foods.

Sample Collection

For each batch of each type of unit food prepared for each diet throughout the feeding period, do the following:

1. Randomly select one (1) unit and
2. Place unit into a zip-lock bag (There should be only one unit in each zip-lock bag)
3. Enter in the appropriate spaces on a cryogenic label (provided): the name of your Center, the unit food name, Diet (D, E, or F), batch preparation date, sampling date (=current date), and your initials.
4. Affix label to the sample bag, **INSIDE**.

NOTE: It is very important to place the label inside the bag, as the label may detach at -20°C.

5. Seal each bag completely and check seal integrity.
6. Freeze and hold all samples at -20°C or lower prior to shipment.

Please return any unused labels and ziplock bags to the FALCC at the end of the feeding period along with sample shipment (thank you).

SHIPPING

******* DO NOT SHIP ON FRIDAY! *******

DO NOT LET PACKED COOLERS SIT AT AMBIENT TEMPERATURE FOR AN EXTENDED TIME PERIOD PRIOR TO FED EX PICK-UP

1. Assemble all samples to be shipped: **FROZEN solid (at least OVERNIGHT at -20°C) prior to shipment.**
2. Ensure that each bag is completely sealed and properly labeled.
3. Fill out a sample transfer form (#F001). Include all required information (see sample form included); **there should be one entry for each sample enclosed in the cooler.** Make a copy of the form for your records.
4. Place all bags in the cooler, then pack wads of brown paper, newspaper or other cushioning material around them.
5. Place a layer of brown paper, newspaper, or other cushioning material on top of containers, **then** add a **minimum of 5 pounds of dry ice.**

USE CAUTION WHEN HANDLING DRY ICE; WEAR APPROPRIATE PROTECTIVE APPAREL AND INSULATED GLOVES.

6. Pack wads of newspaper or brown paper to fill out cooler and prevent movement.
7. Place completed sample transfer form (#F001), Deviation from SOP (Form(s) #F002, (if any), and a **copy** of the Unit Food Batch Preparation Log (Form #F031) in a sealed zip-lock bag (to protect from moisture), and place in cooler, on top.
8. Tightly seal the lid of the cooler with packing tape around seam.
9. Fill out all information on the dry ice stickers (included in shipping kit) required for Federal Express shipping: Make sure to include your **complete** address and make sure that the dry ice weight agrees on all stickers for the same cooler.
10. Affix a pre-addressed pre-paid FedEx shipping label to the box, and send via Federal Express **overnight delivery** to FALCC:

[name]
Dept. of Biochemistry
[name]
Virginia Tech
Blacksburg, VA 24061-0308

11. **Notify FALCC of shipment:** [contact] or [contact] or E-mail: [contact]

5.8.7 Procedure for Collection and Shipping of Fat Blend Samples

PROCEDURE FOR COLLECTION AND SHIPPING OF FAT BLEND SAMPLES- DELTA Protocol 2 DIET MONITORING

**Food Analysis Laboratory Control Center (FALCC)
Standard Operating Procedure**

SOP #1031
Revision: (New)

01-MAR-95

Dept. of Biochemistry and Anaerobic Microbiology
Virginia Tech
Blacksburg, VA 24061-0308

**PLEASE READ THIS PROCEDURE COMPLETELY, PRIOR TO
FOOD COLLECTION**

Scope

This procedure applies to collection of unit food fat blend samples for DELTA Protocol 2 diet monitoring (DELTA Protocol 2 (1994-95)).

Purpose

To describe the procedure for collecting unit food fat blend samples for DELTA Protocol 2 and shipping the samples to FALCC for assay, as part of documentation of diet composition.

Overview

The centrally prepared unit food fat blend for each of the three diets (D,E,F) will be sampled twice at each center: one sample taken between feeding periods 2 and 3 and one sample during feeding period 3. The sampling schedule is shown in the table below (DELTA Protocol 2 MOP, 3/95 addition). Each fat blend sample will consist of 10-15 grams of the fat blend, aliquotted after being liquefied according to the procedure for unit food preparation (per MOP). Sample containers will be provided by the FALCC. Fat blend samples will be frozen at -20°C and shipped frozen on dry ice to the FALCC, where they will be stored at -20°C or lower until assayed.

Sampling Schedule for fat blend monitoring.

Center (all diets)	Feeding Per. 1	Feeding Per. 2	Feeding Per. 3
PSU	not sampled	week of 3/5/95	week of 4/23/95
MINN	not sampled	week of 3/12/95	week of 4/30/95
COL	not sampled	week of 3/19/95	week of 5/7/95
PBRC	not sampled	week of 3/26/95	week of 5/14/95

Materials

At Field Center:

fat blend for each diet (D,E,F)
freezer (-20°C or lower)
heavy paper (e.g. brown paper or newspaper)
dry ice

Food Collection and Shipping Materials (supplied by FALCC):

small glass jars with Teflon lined lids (6)
zip-lock bags
labels
cryogenic marker
fat-free powder-free gloves (disposable)
Form #F001 (sample transfer), with example form filled out
Forms #F002 (deviation from SOP)
shipping cooler
packing tape⁴
Federal Express dry ice identification stickers
pre-addressed Federal Express shipping labels (1 per cooler)

NOTE: Follow these procedures exactly. If any deviation occurs in preparation, packaging, sampling, shipping, etc., fill out form #F002 and include it with the food shipment.

TAKE THE SAME CARE SAMPLING AND PACKING SAMPLE FOR ASSAY AS YOU DO IN PREPARING UNIT FOODS for PATIENTS.

Receipt of Shipping Materials:

Make sure you received all items listed above. If there is a discrepancy or if you should need additional labels or supplies, immediately notify the FALCC at [name], or [contact] or E-mail: [contact].

⁴NOTE: The FALCC will supply each Field Center with a reasonable amount of packing tape for shipping foods to the FALCC - please reserve the tape for this use only.

A. Sample Collection

Sample the fat blend once for each diet (D,E,F) at each of the times specified in the Table on p. 3, as follows. Wear clean powder free gloves (provided) during sampling.

1. Liquefy fat blend according to MOP, as if portion were being taken for preparation of unit foods.
2. Aliquot 10-15 grams of the liquefied blend into one of the clean glass jars provided, **using the same aliquotting technique employed for weighing fat blend for unit food recipe.**
3. Enter in the appropriate spaces on a cryogenic label provided: the name of your Center, Diet (D, E, or F), sampling date (=current date), lot number of fat blend (if any), and your initials.
4. Seal jar tightly and **tape completely around jar/lid seam with packing tape.**
5. Affix label to jar. NOTE: If oil has gotten on outside of jar, may have to clean outside of jar so label will stick. **Make sure lid is securely sealed first.**
6. Place jar into a zip-lock bag and seal bag. Jar is placed inside bag so label will stay with sample if it were to fall off the jar.
7. Freeze and hold all samples at -20°C or lower prior to shipment.

B. SHIPPING

NOTE: Ship fat blend samples along with a menu shipment (FALCC SOP #1027) or unit food shipment (FALCC SOP #1030) to save on shipping costs.

1. Make sure lids are sealed tightly and **taped** onto sample jars to be shipped.
2. Wrap jars in brown paper, newspaper, or other wrap to prevent breakage.
3. Make sure to enter each sample on the sample transfer form (#F001) enclosed with the shipment.

NOTE: Enter all items in the shipment (menus and fat blend samples) individually on a single sample transfer form.

4. Follow procedure for menu or unit food shipment (FALCC SOP #1027 or #1030). Make sure to include deviation forms, if any, for the fat blend samples.

If you have any questions, contact FALCC: [contact]; [contact]; E-mail: [contact]

5.9.2 Missed meals

If a participant is absent for a meal, without a valid reason, he/she may be dismissed from the study. If the participant did not eat any non-study food during the absence, a replacement meal may be provided to be eaten during the remainder of the day.

5.9.3 Food that is left

If the participant is still at the feeding site, give any food that is left back to the participant to eat. If the participant cannot eat all of the meal, it may be packaged for later consumption or it may be added to the next meal. Foods that cannot be safely or aesthetically saved for another meal should be discarded and a replacement provided. Food that is not eaten by the end of the day should be recorded on the form DDD by the kitchen staff or on form FBI by the participant.

5.9.4 Illness

Illnesses that interfere with dietary compliance should be reported immediately to the study coordinator.

5.9.5 Special Requests for single meal carry out

Centers have the option of responding to special requests for packed meals and each center should develop its specific policy. It is important that participants understand the limitations of this policy at the outset. Following are policy guidelines from 3 centers.

Figure 5.9.5.1 PSU Policy for Special Request Packed Meals

PSU Policy for Special Request Packed Meals

Dear DELTA Participant,

Welcome to DELTA II and thank you very much for participating in our large multi-center feeding study.

This is a reminder that you have **agreed** to eat only foods provided by the center and not to eat any additional foods not provided by us. You have also **agreed** to come for your on site meals during the designated hours throughout the whole study. If you need a take-out meal(s) for an unforeseen event, we will evaluate the situation and try to accommodate you.

We need **3 work days** advance notice if it is impossible for you to come for one day or less.

We need **5 work days** advance notice if it is impossible for you to come for more than one day.

An advance notice **does not guarantee** that your request will be granted.

If your life circumstances change in such a way that you will request packed meals very frequently, the central diet subcommittee will re-evaluate your whole file and you may be discontinued from the study.

Many thanks in advance for your cooperations and understanding!

Sincerely,

Principal Investigator

Figure 5.9.5.2 PBRC Policy for Special Request Packed Meals

PBRC Policy for Special Request Packed Meals

- 1) The nurse coordinator will outline our expectations with the participants during the recruiting processing.
- 2) The dietetic coordinator will meet with the participants during Screening 3 to review the menus and discuss our expectations.
- 3) There will be an orientation meeting with the PI, the nurse coordinator, and the dietetic coordinator for all participants before feeding begins. At this meeting, the "Kitchen Connection" brochure will be reviewed, our expectations will be reaffirmed, and questions will be answered.
- 4) The established guidelines are:
 - a) A participant may take-out 2 "on-site" meals during each diet period.
 - b) Because food safety is our greatest concern, a participant is restricted to a maximum of 3 consecutive days of take-out meals.
 - c) A "Take-Out Meal Request" will be completed and approved by both the nurse and the dietetic coordinators. (See attached).
 - d) For compliance assessment, a participant will be expected to return all food containers and uneaten foods to the metabolic kitchen.
 - e) Participants can take-out more meals than allowed only when approved by the PI, the nurse coordinator, and the dietetic coordinator. This procedure will allow for emergencies and for other special cases.

Figure 5.9.5.3 Take Out Meal Request (PBRC)

**TAKE-OUT MEAL REQUEST
PENNINGTON BIOMEDICAL RESEARCH CENTER**

(Participant name/ID) _____, enrolled in the
_____ study requests permission to take-out the following meals on the
dates specified below:

Date: _____	B	L	D	Snack
Date: _____	B	L	D	Snack
Date: _____	B	L	D	Snack

The meals should be ready by _____ (time) on _____ (date).

(Participant name/ID) _____ has been informed of
his/her responsibility for handling the food in a prudent manner to assure food safety.
He/She also has been told to return the empty food containers and any uneaten foods to the
metabolic kitchen for compliance assessment.

Study Coordinator

Date

Dietetic Coordinator
Date

Figure 5.9.5.4 Columbia Policy for Special Request Packed Meals

Columbia Policy for Special Request Packed Meals

Dear DELTA Participant,

The first weekend of the DELTA study is just around the corner. We will be packing the following meals for you:

Saturday's - Breakfast
Lunch
Dinner
Snack

Sunday's - Breakfast
Lunch
Dinner
Snack and

Monday's - Breakfast
Lunch

You are allowed to eat only one meal on your own with our guidelines.

THE "FREE" MEAL COULD BE EATEN AS DINNER IN PLACE OF SATURDAY'S LUNCH OR SUNDAY'S LUNCH.

Please let us know by Wednesday each week if you are planning to eat on your own.

WEEKDAY TAKE-OUT MEAL GUIDELINES

1. You may take-out 1 "one-site" meal during each diet period.
You must request 3 days ahead of time for the take out-meal to [name] or [name].
2. It is your responsibility to keep the food safe.

PLEASE REFRIGERATE THE FOOD IMMEDIATELY.

Please bring empty containers on Monday or the following day.

Please complete the 'PACKED MEAL FORMS' and give it back to the DELTA Staff.

All of you will be given food records for the weekend. On these food records please write down everything you eat and drink on Saturday and Sunday, and return it to us when you come for your lunch on Monday. We will weigh you every Monday and Thursday before lunch.

Please follow the guidelines and instructions carefully as weekend eating is just as important as a weekday.

Thank you for your cooperation.

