5.9.9.1 Emergency Meal Plans

Columbia

Most of our participants live around the dining facility, so it is convenient for them to come or have their friends pick-up their meals. For those who live far away we pack meals. We also use "free meal" allowance during the week instead of the weekend.

Pennington (PBRC)

At PBRC, advance warning of natural disasters (heavy rain or hurricanes) is expected. In the event of pending flooding, meals will be prepared in advance and packaged for take-out. The participants will take their meals with them before the event occurs. If a participant is unable to leave their home, every effort will be made to deliver the meals to them.

Minnesota

In the event that an overnight major snowfall or severe temperature/wind chill is forecast where individuals are advised to stay in their homes due to danger encountered with travel or exposure, the University of Minnesota DELTA Center will pack meals for the following day. Breakfast and the pre-packed lunch will be sent with participants whose job position would not necessitate their coming to the University the following morning. (A number of employees are considered critical to the function of the University medical departments, and are exempt to such an advisory.) In the case of an overnight snowfall, it would be likely that most participants would be able to come to the center for their evening meal the next day as snow removal takes place in only a matter of hours in this area of the country. Participants who are living long distances from the center AND who would have no other purpose to come to the center will be given their packed breakfast and lunch meal along with Healthy Choice™ entree(s) and the remaining fruit, vegetable, bread and fat items that would have otherwise made up that evening meal. The DELTA kitchen is considered a

medical research unit and is exempt to days/shifts canceled due to weather conditions. Employees are available to serve meals for those participants who are willing and able to eat at the center.

Penn State

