5.11 SELF-SELECTED MEAL

Participants are allowed one self-selected meal in place of the Saturday evening meal. Participants are given guidelines to select a meal that is 30% fat. See Figure 5.11.1. Use of the self-selected meal is optional. Participants may choose to have all weekend meals provided by the field center.

Each center will use its own procedure for ascertaining the composition of the self-selected meal. Examples of good choices from common restaurant types can be found on pages 117-120.

Figure 5.11.1 Guidelines for the Self-Selected Saturday Evening Meal

DELTA Guidelines for the Self-Selected Saturday Evening Meal

To prevent your self-selected meal from interfering with the DELTA Study results, **please use the following guidelines in making your selections.**

1. Avoid fried and breaded foods such as fried chicken, breaded fish, french fries, etc.
2. Remove all visible fat from meat and skin from chicken before eating.
3. Avoid the use of gravy, cream sauces, cheese, sauces, and butter. Use margarine and limit the amount to one-two teaspoons.
4. Limit the use of oils, salad dressings mayonnaise, and the like to one-two tablespoons.
5. Limit meat serving size to four-six ounces or one-two pieces of chicken (skin removed).
6. Avoid high fat meats and cheeses. Hamburgers should be without cheese. Pizza should be vegetable or ground beef with usual (not extra) amount of cheese.

Examples of foods that would be considered good choices for some common restaurant types are listed below:

Chinese Restaurant

- Good Choices:** Won Ton Soup
Chicken or Shrimp Chow Mein, Chop Suey, Moo Goo Gai Pan
Chicken or seafood and vegetable dish
Steamed rice
Steamed or stir fried vegetables
Fortune cookie, sherbet
Tea or other allowed beverages
- Avoid:** Egg Drop Soup
Egg Rolls, Fried Wonton, Ribs
Egg Foo Young
Fried Rice
Menu items made with ingredients fried in hot oil

Italian Restaurant

Good Choices: Cooked spaghetti or pasta
Tomato sauce
Meatballs (limit to 3-4, 1" diameter)
Salad greens, tomato, onion, fresh vegetables
Italian or French dressing
Fresh fruit
Plain hard rolls, French bread
Allowed beverages

Avoid: Alfredo, cream and cheese sauces
Cheese based main dishes
Pre-buttered breads and rolls
Feta cheese (in salads, etc)
Excessive margarine, olive oil, salad dressing, cheese

Mexican Restaurant

Good Choices: Chicken taco, tastado or fajita
Tortillas made with cornmeal or soft flour tortillas
Salad greens, tomato, onion, avocado
Spanish rice

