IF A PARTICIPANT REQUESTS TO BE ALLOWED NOT TO EAT MEAT ON FRIDAYS DURING LENT, he/she may do the following:

1. The participant may remove the meat from the Friday lunch sandwich and not eat it. This will be recorded on the Participant Food and Beverage Intake Report (FBI) under #3; and will consequently get recorded onto a DELTA Diet Deviation Form and the Compliance Check Sheet for that participant.
2. At Friday dinner the participant may take the self-selected meal option but **MUST** take the DELTA Friday night meal as a packed meal to eat for the Saturday night dinner. This exchange of meals will be recorded as a Protocol Deviation in the Center's DELTA Log Book maintained in the kitchen at each site.

This plan should minimize deviations from the diets while making allowances for our participants religious convictions. **HOWEVER, APPROPRIATE AND ACCURATE DOCUMENTATION OF THE DEVIATIONS IS REQUIRED TO INSURE THE CONTINUED INTEGRITY OF OUR STUDY.**

Call [name], [name], [name], or me if you have questions or concerns about these decisions.

TABLE OF CONTENTS

CHAPTER 6: Postprandial Studies

6.0	Postprandial Studies	1
6.0.1	Guidelines for the Preparation and Administration of the Test Meal	1
6.0.2	Sampling for Fat Load Test	2
	Figure 6.0.2.1 Nutrient Values	3
	Figure 6.0.2.2 Nomogram for Calculating Surface Area	4
6.1	Preparation and Delivery of Meal Test	5
	Figure 6.1.1 Adding Unit Foods to Postprandial Menus	6

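### Columbia's local texts allow the self-selected meal on a day, and in place of a study meal, that Section 5.11 does not allow, so it could be the last meal before an endpoint draw

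*Protocol*

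**What the plan says.** **Study-wide rule.** Section 5.11 states: "Participants are allowed one self-selected meal in place of the Saturday evening meal". The accompanying guideline sheet (Figure 5.11.1) is titled for that meal. On content, "Participants are given guidelines to select a meal that is 30% fat", and "Each center will use its own procedure for ascertaining the composition of the self-selected meal".

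**Columbia, weekend.** The letter in Figure 5.9.5.4 says "You are allowed to eat only one meal on your own with our guidelines", and then that the free "MEAL COULD BE EATEN AS DINNER IN PLACE OF" Saturday's or Sunday's lunch.

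**Columbia, weekday.** Under Emergency Meal Plans (5.9.9.1), Columbia reports using the free-meal "allowance during the week instead of the weekend".

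**The study's handling of a similar move.** The Lent memo in Appendix II of Chapter 5 lets a participant who asks take the self-selected meal on Friday and eat the packed Friday study dinner on Saturday. It adds: "This exchange of meals will be recorded as a Protocol Deviation in the Center's DELTA Log Book maintained in the kitchen at each site".

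**Endpoint draws.** Chapter 8 (II.A and Appendix I, Tables 1 and 4) has fasting blood taken once a week in weeks 5, 6 and 7 of each diet period, in the morning, after at least 8 hours without food. The draw date on the Participant Weekly Monitoring form is left blank for completion; no weekday is set.

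**The concern.** The self-selected meal is the one planned weekly meal that the study does not supply, weigh or assay. If it is confined to Saturday evening, at least a full day of study food separates it from any weekday draw. Columbia's wording removes that separation at one of the four centers. The primary endpoints in Section 1.0.2 include triglycerides, factor VII, and fasting insulin and glucose, all measured at these draws. The only dietary restriction before a draw, apart from the fast, is the 48-hour bar on alcohol in 5.6.1; nothing comparable covers the free meal.

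The same event would also be classed differently by center. Moving the meal off Saturday is a protocol deviation under the Lent memo and an ordinary option under Columbia's letter, so a count of deviations by center would not be comparable.

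**Working it through.** There is no planned figure to reproduce. The check is a comparison of texts followed by clock arithmetic.

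**1. The texts side by side.**

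| Source | Day allowed | Study meal displaced | Logged as deviation? |
|---|---|---|---|
| 5.11 | Saturday | Dinner | Not applicable (standard) |
| Figure 5.9.5.4 (Columbia letter) | Saturday or Sunday | Lunch; free meal eaten as dinner | Not requested |
| 5.9.9.1 (Columbia emergency plan) | Weekday | Not stated | Not requested |
| Lent memo, Appendix II | Friday, on request only | None at dinner: Friday's study dinner moves to Saturday | Yes |

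The Columbia letter therefore departs from 5.11 on two points, the day and the meal displaced. Section 5.9.5 does invite each center to set its own policy, but on requests for packed meals. It does not hand over the day of the self-selected meal.

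**2. Time from the free dinner to a draw.** Inputs: the draw window is 6 to 10 am (Phlebotomy Processing Form; Chapter 8, Appendix IV), although II.A gives 7 to 10 am. Dinner is assumed to end at 6:30 pm, borrowed from the Minnesota dinner hours in 5.5.1, because no Columbia hour is given.

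- Saturday dinner to a Monday draw: 5.5 h to Saturday midnight + 24 h Sunday + 6 to 10 h = 35.5 to 39.5 h, with Sunday's study meals in between.
- Sunday dinner to a Monday draw: 5.5 + 6 to 10 = 11.5 to 15.5 h.
- Weekday dinner to a draw the next morning: the same 11.5 to 15.5 h.

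Both shorter intervals exceed the 8-hour fast, so the fasting rule would not stop such a draw. With the 7 am start, the lower limits become 36.5 h and 12.5 h.

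**3. What would record it.** The Phlebotomy Processing Form asks for hours since last food and since last alcohol. It does not ask whether the last meal was study food.

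**4. Ceiling on exposure.** Table 1 of Chapter 2 assumes 5 + 6 + 14 = 25 Columbia participants out of 100. With 3 draws in each of 3 periods, Columbia contributes 25 × 9 = 225 of 900 planned draws. This is simply every draw at that center. The number preceded by a free dinner cannot be computed, because neither uptake of the optional meal nor the draw weekday is given.

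**The case against.** Several counter-arguments have force.

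- **Monday draws at Columbia may be uncommon.** The same letter packs Monday's breakfast for home, asks for weekend food records when participants come for Monday lunch, and weighs them before lunch. That points to a midday first contact, after the draw window. It does not exclude a Monday draw, and the letter is not wholly consistent, since it also packs Monday's lunch. This limits how often the Sunday route would matter.
- **Weekday use is not routine.** The sentence sits in the emergency plan, and 5.9.9 reserves emergency meals for rare, unplanned events. This stands: weekday use is an exception and not on a par with the Sunday option.
- **The meal is not without control.** Guidelines apply, each center must ascertain its composition, Columbia collects weekend food records, and 5.9.1 requires a log of unusual circumstances. This stands too. The accurate description is a meal not supplied or weighed by the study.

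A reader might infer that the 30% fat target pulls Diets D and E (37% fat) toward Diet F (30%) and so shrinks the E–F contrast at Columbia. The documents do not support that. The target and the weekly allowance are the same at every center, so moving the meal to another day leaves the number of such meals unchanged. Each participant also follows a diet sequence, so Columbia's rule applies under all three diets. Only a possible last-meal effect is specific to Columbia.

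**Conclusion.** The contradiction is real and stands in the current text: Section 5.11, Figure 5.9.5.4 and the Columbia paragraph of 5.9.9.1 cannot all be followed, and the Lent memo shows that the study itself counts a comparable move as a deviation. As written, a Sunday free dinner, or an emergency weekday one, could be the last intake before a primary-endpoint draw at Columbia. That is a possibility created by an unfixed draw weekday and the absence of any bar; the documents do not say that it happens.

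A reader might go on to infer that a sizeable share of Columbia's 225 planned draws is affected. No such share can be derived, and Columbia's Monday routine argues for a small one. The clock intervals rest on the assumed 6:30 pm dinner, but the conclusion does not depend on it: any dinner finished at least 8 hours before the draw satisfies the fast. The point is modest in size but worth correcting, because the remedy is nearly free.

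**What to change.** 1. Reconcile Figure 5.9.5.4 and the Columbia paragraph of 5.9.9.1 with Section 5.11, so that one rule on both the day and the study meal displaced holds at all four centers.
2. Log any exception to that rule as a protocol deviation at every center, as the Lent memo already does.
3. In weeks 5 to 7, schedule the free meal so that it does not fall on the evening before that participant's draw. If it does, record it with the draw, for example by one added item on the Phlebotomy Processing Form.

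The existing three-day rescheduling rule might look like a ready remedy, but it should not be used here. It was written for participants who have not fasted or who arrive outside the draw window. The menu schedule in Figure 5.4.7.1 ends each feeding period on a Friday, so a late week-7 draw postponed by up to three days could fall after the study diet has stopped.

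The cost is a change of letter wording, one item to record, and slightly less flexibility for Columbia participants.
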